4.7.6.4 CCI

CCI documented on the CCI of the CCI F are presumed to include episodes of pneumonia given the requirement for intravenous antibiotics. Data will be reviewed during the blind review meeting and documented in the Blind Data Review and Analysis Sets Report.

A CCI will be defined as treated with systemic antibiotic therapy if a treatment is recorded in the Systemic Antibiotic Therapy form of the eCRF.

The number of CCI will be analysed using a negative binomial model in the same manner as described for the primary endpoint (which includes all CCI) in Section 4.7.4. The annualised CCI

CONFIDENTIAL

Sponsor:	Zambon S.p.A.	Protocol Number:	Z7224L02
----------	---------------	------------------	----------

CCI [redacted] rate estimates will be extracted for each treatment group from the model along with the rate ratio and its 95% CI and p-value..

The above summary/analysis will be performed using the mITT Population.

4.7.6.5 CCI [redacted]

The time to first severe NCFB pulmonary exacerbation will be analysed in the same manner as for the CCI [redacted] and tested using a log-rank test as detailed in Section 4.7.6.1.

The above summary/analysis will be performed using the mITT Population.

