3.7 Randomisation

At Visit 2, eligible subjects will be randomised using the interactive web response system (IWRS) according to a pre-specified randomisation scheme such that they either receive colistimethate sodium or placebo. Site and use of stable concomitant therapy with oral macrolides (e.g. azithromycin or erythromycin or clarithromycin) (Yes/No) will be considered as factors for balancing randomisation, i.e. stratification factors. Thus, within each site, subjects

CONFIDENTIAL

Sponsor:	Zambon S.p.A.	Protocol Number:	Z7224L02
----------	---------------	------------------	----------

with oral macrolides use will be randomised independently from subjects without use of macrolides, to receive colistimethate sodium or placebo in a 1:1 ratio. The randomisation within each site and nested level macrolide use will be done with blocks to guarantee a good balance between colistimethate sodium and placebo at any stage of the enrolment.

Note: according to Exclusion Criterion 15, the decision on whether stable concomitant antibiotic therapy with oral macrolides will be administered to a subject or not will have been taken at least 30 days prior to the Screening Visit (Visit 1). The treatment with oral macrolides should be continued throughout the trial in order not to jeopardize the study results.

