4.7.6 Methods of Analysis for Secondary Endpoints

4.7.6.1 CCI [REDACTED]

The CCI [REDACTED] will be calculated as the time in days from the date of randomisation to the date at which the first pulmonary exacerbation occurs.

- CCI [REDACTED] (days) = start date of first NCFB pulmonary exacerbation - date of randomisation. (It should be noted that this differs slightly from the CCI [REDACTED] CCI [REDACTED] CCI [REDACTED] CCI [REDACTED]. For time-to-event endpoints, generally the + 1 is not included because this overestimates the time by 1 day for every event.)

Subjects completing the trial without CCI [REDACTED] or who are discontinued prematurely CCI [REDACTED], will be considered as censored at the time of their last follow-up, i.e. at the date of treatment completion/discontinuation. For the analysis, the following formula will be applied:

- Censoring time (days) = (date of treatment completion/discontinuation - date randomisation)

The number of subjects with a first CCI [REDACTED] events will be summarised.

CONFIDENTIAL

Sponsor:	Zambon S.p.A.	Protocol Number:	Z7224L02
----------	---------------	------------------	----------

A Cox proportional hazard regression model will be applied to the data to provide an estimate of the hazard ratio (HR), colistimethate sodium:placebo. The model will include treatment group, country, as detailed in Section 4.9.1, and use of stable concomitant therapy with oral macrolides as covariates. The HR and its associated 95% CI and p-value will be extracted from the model and presented. A supportive analysis will be conducted using the log-rank test and the associated p-value will be presented.

Kaplan-Meier estimates in each treatment group will be presented: median time to CCI, 25th and 75th percentiles and the corresponding CIs will be tabulated. The number of CCI-free subjects at the beginning of the period, the cumulative number of subjects with CCI at the end of the period and the estimated rates of pulmonary exacerbations at the end of the period with the associated 95% CIs will be presented by treatment group for the following study periods: (0-28] days, (28-90] days, (90-180] days, (180-270] days and (270 days - End of Treatment] as supportive statistics.

The estimate of the survivor function in each group will be displayed graphically using a Kaplan-Meier curve.

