4.14 Algorithms/SAS Codes

The SAS codes for descriptive statistics and frequency counts detailed below are examples only and other procedures may be used, if appropriate.

- **Tables that need descriptive statistics – continuous variables:**

```
PROC UNIVARIATE DATA=dset NOPRINT;
  VAR var1 var2 var3 ...varn;
  BY byvar; (optional)
  OUTPUT OUT= outset
  N=n MEAN=mean MIN=min MAX=max MEDIAN=median STD=std *Q1=q1
  Q3=q3; *Include Q1 and Q3 for CCI data only;
RUN;
```

- **Tables that need frequency counts:**

```
PROC FREQ DATA=dset NOPRINT;
  BY byvar; (optional)
  TABLES var1*var2 /out= outset;
RUN;
```

- **Tables that need T-Test;**

```
PROC TTEST DATA=dset;
  CLASS var1;
  VAR var1N;
RUN;
```

- **Tables that need exact 95% CIs for risk difference between groups for proportions and Fisher's Exact:**

```
PROC FREQ DATA=dset;
  BY byvar; (optional)
  TABLES var*treatment / MEASURES RISKDIFF EXACT ALPHA=0.05;
  EXACT MEASURES;
  OUTPUT OUT= outset EXACT MEASURES RISKDIFF;
  WHERE wherever; (optional)
RUN;
```

- **Tables that need 95% CIs within group for binomial proportions:**

```
PROC FREQ DATA=dset;
  BY byvar; (optional)
  TABLES var1;
  EXACT BINOMIAL;
  OUTPUT OUT= outset BINOMIAL;
RUN;
```

- **Tables that require analysis of (co)variance and 95% CIs between arms for continuous variables:**

```
PROC GLM DATA= dset OUTSTAT=outset;
  CLASS treatment psite med;
```

CONFIDENTIAL

Sponsor:	Zambon S.p.A.	Protocol Number:	Z7224L02
----------	---------------	------------------	----------

MODEL change = treatment psite med baseline/ SOLUTION;
LSMEANS treatment / STDERR PDIFF CL OBSMARGINS;
BY byvar; (optional)
WHERE wherever; (optional)

RUN;

Notes:

- Psite represents the country, as detailed in Section 4.9.1;
- Med represents use of stable concomitant therapy with oral macrolides (e.g. azithromycin or erythromycin or clarithromycin) (Yes/No);
- Change represents the change from baseline of the variable;
- Baseline represents the baseline value of the variable;
- Treatment order: 1= Colistimethate Sodium, 2= Placebo.

• **Tables that require Kaplan-Meier estimates and log-rank test:**

PROC LIFETEST DATA=dset OUTSURV=LIFE METHOD=KM timelist=(0 28 90 180 270 EoT) reduceout;

*TIME time*event (1);*
ID subject;
STRATA treatment;
WHERE wherever; (optional)

RUN;

Notes:

- Time represents the time to event or time to censoring;
- Event represents the censoring indicator (1 = censored);

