- EoT should be replaced by the last time (in days) to event >270 days (if any);

• **Tables that require Cox proportional hazards model and 95% CIs of hazard ratios between treatments:**

PROC PHREG data=dset;
CLASS treatment psite med;
*MODEL time*event(1) = treatment psite med / ties=exact;*
HAZARDRATIO 'Col. Sodium vs Placebo' treatment / cl=both;
BY byvar; (optional)
WHERE wherever; (optional)

RUN;

Notes:

- Psite represents the country, as detailed in Section 4.9.1;
- Med represents use of stable concomitant therapy with oral macrolides (e.g. azithromycin or erythromycin or clarithromycin) (Yes/No);
- Time represents the time to event or time to censoring;
- Event represents the censoring indicator (1 = censored);
- If the option ties=exact requires a considerable amount of computer resources, the Efron approximation will be used (*ties=efron*).
- Treatment order: 1= Colistimethate Sodium, 2= Placebo.

CONFIDENTIAL

Sponsor:	Zambon S.p.A.	Protocol Number:	Z7224L02
----------	---------------	------------------	----------

- **Tables that require negative binomial modelling, including 95% CIs of treatment ratios:**

```
PROC GENMOD data = dset;
  CLASS treatment psite med;
  MODEL count = treatment psite med / offset=log_years link=log dist=negbin wald
  type3;
  ESTIMATE 'Col. Sodium / Placebo' treatment 1 -1 / exp;
  lsmeans treatment / ilink cl diff exp om;
  BY byvar; (optional)
  WHERE wherever; (optional)
RUN;
```

Notes:

- Psite represents the country, as detailed in Section 4.9.1;
- Med represents use of stable concomitant therapy with oral macrolides (e.g. azithromycin or erythromycin or clarithromycin) (Yes/No);
- Count represents the total number of exacerbations for each patient;
- log_years represents the logarithm of the follow-up time in years;
- Treatment order: 1= Colistimethate Sodium, 2= Placebo.

- **Tables that require linear mixed model for repeated measures and 95% CIs of differences between treatments:**

```
PROC MIXED data = dset;
  CLASS treatment visit psite med sub;
  MODEL change = treatment visit treatment*visit psite med baseline/ s ddfm=kr;
  REPEATED visit / subject=sub type=un r;
  LSMEANS treatment treatment*visit / om at means cl slice=visit;
  LSMESTIMATE treatment
  'Col. Sodium / Placebo' 1 -1 / cl;
  LSMESTIMATE treatment*visit
  'Col. Sodium / Placebo: Visit 4' 1 0 0 0 -1 0 0 0,
  'Col. Sodium / Placebo: Visit 5' 0 1 0 0 0 -1 0 0,
  'Col. Sodium / Placebo: Visit 6' 0 0 1 0 0 0 -1 0,

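### SAP 4.7.6.5 names as the test for time to first severe exacerbation a log-rank that 4.7.6.1 treats as supportive and 4.14 codes without macrolide use or country

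*SAP*

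**What the plan says.** SAP 4.7.6.5 makes two statements about time to first severe exacerbation. The first is general: "The time to first severe NCFB pulmonary exacerbation will be analysed in the same manner as for the" endpoint of 4.7.6.1. That endpoint's name is redacted, but the formula given there shows it is time to first exacerbation. The second names the test: "tested using a log-rank test as detailed in Section 4.7.6.1".

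In 4.7.6.1 the Cox model supplies the hazard ratio, its 95% CI and a p-value: "The model will include treatment group, country, as detailed in Section 4.9.1, and use of stable concomitant therapy with oral macrolides as covariates". The log-rank comes after it: "A supportive analysis will be conducted using the log-rank test and the associated p-value will be presented".

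Section 4.14 gives the code. The log-rank procedure has "STRATA treatment" and no other stratum. The Cox procedure has "treatment psite med / ties=exact", where `psite` is country and `med` is macrolide use. Under 3.7, site and stable oral macrolide use "will be considered as factors for balancing randomisation, i.e. stratification factors". Section 4.9.1 groups sites under country because they are too many to fit.

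The table list in 5.3.3 gives Table 14.2.2.7.1 for the severe exacerbation rate (negative binomial) and Table 14.2.2.7.2 for the time endpoint (Kaplan-Meier estimates).

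**The concern.** The two halves of 4.7.6.5 point to different p-values. Its general statement leads to the adjusted Cox model. Its specific statement leads to an unadjusted log-rank that the cited section ranks below the Cox model. Section 4.7.5 tests secondary endpoints in a fixed order and lets no test count unless every earlier one is significant, so each step needs one p-value fixed in advance.

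The named test also sets aside information used elsewhere. The primary analysis (4.7.4), the time-to-first analysis (4.7.6.1), the negative binomial analysis of 4.7.6.4 and the ANCOVA of 4.7.6.6 all adjust for country and macrolide use. If these factors are prognostic, leaving them out of the log-rank costs some power. A table list with Kaplan-Meier output alone would also leave the adjusted between-arm estimate without a clear home.

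**Working it through.** The SAP states no event count, hazard ratio or power for this endpoint, so there is no plan figure to reproduce. The check sets the text side by side and then sizes the effect on assumed inputs.

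**1. Text**

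| Item | 4.7.6.1 | 4.7.6.5 |
|---|---|---|
| Overall approach | Adjusted Cox, Kaplan-Meier, Weibull | As 4.7.6.1 |
| Log-rank | Supportive | Named as the test |
| Factors in the log-rank code | None beyond treatment | Same code |
| Cox table | 14.2.2.2.1 to 14.2.2.2.4 (names redacted) | None clearly listed |

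Assigning the four Cox tables to 4.7.6.1 is an inference, but a strong one. One is for the per-protocol population, and 4.7.6.5 is confined to mITT. Two are the antibiotic-use versions that 4.7.6.1 describes.

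**2. Log-rank against adjusted Cox**

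From the SAP: 287 randomised (3.9), 1:1 allocation (3.7), two-sided 0.05 (4.1.4). Assumed: 0.3 severe events per year, hazard ratio 0.55, 35% on macrolides, 7 countries, exponential times, half the subjects censored at 1 year and half uniformly between 0.25 and 1 year.

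| Prognostic effects (assumed) | Log-rank | Cox |
|---|---|---|
| Moderate: macrolide HR 0.7, country log-SD 0.4 | 50.3% | 50.8% |
| Strong: macrolide HR 0.5, country log-SD 0.8 | 45.9% | 49.7% |

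These are powers from 1,500 simulated trials each. A separate run of 1,000 trials gave 49.6% against 50.2% (moderate) and 47.4% against 52.7% (strong). In that run the two tests fell on opposite sides of 0.05 in 4.6% of trials with no prognostic effects, 8.4% with moderate and 11.7% with strong ones.

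**3. Unstratified against stratified log-rank**

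The statistic is Z = Σ e(g − p) / √Σ e p(1 − p). Here e marks an event, g is the arm, and p is the share of the risk set in that arm. The stratified version takes the sums within strata. Assumed: 287 subjects, baseline severe rate 0.2 or 0.4 per year, 30% on macrolides, macrolide HR 1 to 3, 8 country groups with log-hazard SD 0 or 0.7, true hazard ratio 0.5, censoring at the earlier of 1 year and a uniform time on 0.25 to 1.6 years, 1,500 trials each. Selected powers:

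| Rate | Macrolide HR | Country SD | Unstratified | By macrolide | By macrolide × country |
|---|---|---|---|---|---|
| 0.2 | 1 | 0 | 47.2% | 47.2% | 46.5% |
| 0.2 | 2 | 0 | 57.0% | 57.4% | 55.5% |
| 0.2 | 3 | 0.7 | 61.9% | 64.0% | 65.7% |
| 0.4 | 2 | 0.7 | 78.8% | 79.5% | 84.1% |
| 0.4 | 3 | 0 | 85.6% | 88.9% | 87.3% |
| 0.4 | 3 | 0.7 | 82.3% | 84.8% | 86.9% |

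Over all 12 settings the change from unstratified ranged from −0.8 to +3.3 points for macrolide strata alone. For macrolide × country it ranged from −1.5 (57.0 to 55.5) to +5.3 (78.8 to 84.1).

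Type I error ranged from 0.029 to 0.056 unstratified, 0.031 to 0.059 by macrolide, and 0.046 to 0.056 by macrolide × country. The simulation error at 0.05 is √(0.05 × 0.95/1500) = 0.006. The unstratified test is therefore at or below its nominal level, and conservative where the factors are strong.

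**4. Events and the median**

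With the inputs of step 2, before covariate effects, the event probability is 1 − e^(−0.3) = 0.259 on placebo at 1 year and 1 − e^(−0.165) = 0.152 on active (0.3 × 0.55 = 0.165). For the half censored uniformly on 0.25 to 1 year the averages are:

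- placebo: 1 − (e^(−0.075) − e^(−0.3))/(0.3 × 0.75) = 0.169
- active: 1 − (e^(−0.04125) − e^(−0.165))/(0.165 × 0.75) = 0.097

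Expected events are 143.5 × (0.259 + 0.169)/2 + 143.5 × (0.152 + 0.097)/2 ≈ 31 + 18 = 49. At 26% with an event by month 12, the Kaplan-Meier median is not reached. Under a constant hazard, a median within a year needs a severe rate of at least ln 2 = 0.69 per year.

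**The case against.** The strongest reply is that 4.7.6.5 does name one test, that an unstratified log-rank is valid, and that it may be supportive for one endpoint and decisive for another. Log-rank is also the only time-to-event test the protocol names (Summary and 19.4.2, endpoint names redacted). All of that stands. It does not explain why the same sentence first refers the reader to an analysis led by the adjusted Cox model. A plausible cause, though only an inference, is that 4.7.6.1 moved to Cox and the log-rank wording stayed in 4.7.6.5.

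A second reply is that an adjusted Cox model may be too rich for a sparse endpoint. With treatment, macrolide use and 7 countries it has 1 + 1 + 6 = 8 parameters, about 49/8 ≈ 6 events each, and the pooled Other group in 4.9.1 has 3 + 3 + 4 + 1 + 6 + 2 = 19 subjects. This stands, and the fix allows for it.

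Three stronger readings are tempting, and the documents do not support them:

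- A reader might infer that the endpoint would be reported as a p-value with no effect size. The approach carried over from 4.7.6.1 includes a Cox hazard ratio, and its Kaplan-Meier output includes event rates by arm and period with 95% CIs. Table titles do not show full contents either, since no title mentions a log-rank for any endpoint, and the layouts sit in a separate shells document.
- A reader might infer that the hierarchy is broken at this step. The ordered list in 4.7.5 is redacted, so this endpoint's place in it cannot be confirmed.
- A reader might infer a false-positive risk. Step 3 shows the opposite.

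**Conclusion.** The point holds as an inconsistency with a modest cost. Section 4.7.6.5 borrows an adjusted Cox analysis but names as its test the unadjusted log-rank which the cited section ranks second. The code leaves out macrolide use and country, and no Cox table is clearly listed for the endpoint.

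The gain from adjustment is about 0 to 5 points of power. It is practically nil with moderate prognostic effects (50.3% against 50.8%), slightly negative in some settings without country effects, and reaches about 5 points only with strong ones. These figures rest on assumed severe-event rates, macrolide prevalence and prognostic effects, none of which the documents give. The choice between tests can also matter in itself: in the settings simulated they disagreed at 0.05 in about 5% to 12% of trials. The textual findings need no assumption beyond the inference about the redacted Cox table titles.

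**What to change.** 1. In SAP 4.7.6.5, state that the Cox model of 4.7.6.1 (treatment, country, macrolide use) gives the deciding p-value, reported with the hazard ratio and 95% CI.
2. Keep the log-rank as supportive and stratify it by macrolide use, coded `STRATA med / GROUP=treatment`.
3. Add a Cox table for this endpoint, for example 14.2.2.7.3.
4. If the pooled, blinded count of severe events is too small for the country terms, pre-specify the macrolide-stratified log-rank as the deciding test and report the Cox hazard ratio as the estimate. Choose one route and record it before unblinding.

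The cost is one or two sentences, one line of code and one table, with no new data. The small drawback of the first route is sparse country terms, which item 4 covers. A change made after the blind is broken would have to be labelled post hoc under the SAP's own rule in its introduction.

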4.7.6.6 CCI [redacted]

The CCI [redacted] will be presented by treatment group.

The endpoint quantity for each subject will be computed with the following formula:

$$\text{CCI [redacted]} = 365.25 \times \{(\text{follow-up time [days]} - \text{sum of durations of CCI [redacted]}) / \text{follow-up time [days]}\} .$$

Follow-up time will be computed as detailed in Section 4.1.7.

For CCI [redacted] CCI [redacted] [redacted] with a resolution date after the treatment completion/discontinuation, the number of days of duration after the treatment completion/discontinuation, i.e. out of the follow-up period, will be subtracted from the sum of durations of CCI [redacted].

The annualised number of CCI [redacted] days will be compared between the treatment groups using an ANCOVA model including treatment, country, as detailed in Section 4.9.1, and use of stable concomitant therapy with oral macrolides as fixed effects. Least square means in each treatment group, least square mean difference between treatments, their 95% CIs and associated p-value will be estimated. OBSMARGINS option will be used for least square means estimates.

In addition, a summary statistics table will be produced to display:

- For each treatment group:
 - The number of subjects with at least one protocol-defined CCI [redacted], and their:
 - Mean exposure time (months);
 - Total number of CCI [redacted];
 - Mean number of CCI [redacted];
 - Mean duration of CCI [redacted];
 - Total months CCI [redacted].
 - The number of subjects with zero protocol-defined CCI [redacted]s, and their:
 - Mean exposure time (months);
 - Total months CCI [redacted].

CONFIDENTIAL

Sponsor:	Zambon S.p.A.	Protocol Number:	Z7224L02
----------	---------------	------------------	----------

- Overall total months CCI [REDACTED];
- Mean time CCI [REDACTED] (months).
- Difference in mean time CCI [REDACTED] between treatment groups;
- Ratio of mean time CCI [REDACTED] between treatment groups.

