9.6. FOLLOW-UP PHONE CALL (2 WEEKS ± 3 DAYS AFTER END OF TREATMENT)

A follow-up phone call will be performed at 2 weeks ± 3 days after the discontinuation of IMP. The following procedures will be performed during the call:

- documentation of concomitant medications;
- AE monitoring.

If the result of the CCI test at the end of treatment (Visit 7) suggests the subject is CCI, he/she will be called for an extra visit with CCI collection for analysis of CCI.

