4.1.7 Definition of Exposure Time and Follow-up Time

All the efficacy analyses are focused on the endpoints collected during the treatment period. For these analyses, the exposure time will not include the time from end of treatment to the follow-up call.

The exposure time in days will be calculated using the following formula:

CONFIDENTIAL

Sponsor:	Zambon S.p.A.	Protocol Number:	Z7224L02
----------	---------------	------------------	----------

- Exposure time (days) = [date of treatment completion/discontinuation - date of first IMP dose + 1].

The exposure time in years will be calculated using the following formula:

- Exposure time (years) = Exposure time (days) / 365.25.

Date of treatment completion will be the date of End of Treatment Visit.

Date of treatment discontinuation will be the date of End of Study Visit for subjects who discontinued the study before the End of Treatment Visit. In case a subject is lost to follow-up, the date of treatment discontinuation will be the date of last Study Visit.

Date of last exposure will not include any visits/calls after the end of treatment.

The follow-up time in days will be calculated using the following formula:

- Follow-up time (days) = [date of study completion/discontinuation - date of first IMP dose + 1].

The follow-up time in years will be calculated using the following formula:

- Follow-up time (years) = Follow-up time (days) / 365.25.

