4.1.11 Exclusion of Data from the Statistical Analysis

If a subject received the incorrect treatment after being treated with the correct one, all the data collected after the date of the wrong treatment dispensing will be reported in listings and flagged, but not included in the statistical analysis on the ITT, mITT, Safety and PP populations.

Unless stated otherwise, primary efficacy endpoint and related assessments conducted at an early termination visit or unscheduled visit will be included in the statistical analysis, Where not stated differently, other assessments conducted at an early termination visit and unscheduled assessments will not be considered in the statistical analysis, but will be listed only.

Only NCFB pulmonary exacerbations with a start date \geq date of first IMP dose and \leq date of treatment completion/discontinuation will be considered in the analysis.

In case of data excluded from the statistical analysis (in the situations described above but also in other cases, for example: spirometry tests excluded due to technical issues, or assessment not done), the derived variables based on these data will not be calculated. For example, the change from baseline to Visit 5 will not be calculated if the measurement at Visit 5 is excluded from the statistical analysis, or all the changes from baseline will not be calculated if the measurements pre-dose are excluded.

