4.7.4.2 CCI Analysis for Missing Data

In order to assess the potential impact of missing data on the results of the primary efficacy analysis, Copy Reference and Tipping Point CCI analyses using multiple imputation (MI) will be performed on all mITT subjects based on the approach proposed by Keene et al. [1].

Since Promis II was curtailed early, not all subjects are expected to have 365 days follow-up as intended in the original trial design. The expected duration of exposure for some subjects will therefore be shorter than 365 days. Therefore, and prior to unblinding, the expected duration of exposure in years, t_j , will be determined for each subject, $n = 1 \dots j$, individually using their randomisation date, r_j , and the date of study closure, d , where $d = 28\text{FEB}2022$ and $t_j = \min([d - r_j + 1]/365.25, 365/365.25)$. For all subjects with a realised follow-up duration, f_j , shorter than t_j , ie. with $f_j < t_j$, for example, due to early withdrawal or dropout

CONFIDENTIAL

Sponsor:	Zambon S.p.A.	Protocol Number:	Z7224L02
----------	---------------	------------------	----------

at time f_j relative to randomisation, the number of pulmonary exacerbations in the missing period of follow-up, $t_j - f_j$, will be imputed.

The number of potentially missing exacerbations per subject will be imputed to include the following variables: treatment, country, as detailed in Section 4.9.1, and use of stable concomitant therapy with oral macrolides.

The imputation will be performed according to the following strategies:

- (1) Copy reference: imputation of missing data in both randomised treatment groups based on the data distribution of data observed in the placebo group. This analysis mimics the case where discontinued subjects who were randomised to colistimethate sodium are assumed to instantaneously transition to placebo and lose any effect conferred by colistimethate sodium.

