4.13 Changes in Conduct or Planned Analyses from the Protocol

Sections 2.2, 4.4.11, 4.7.5 and 4.7.6.3: The protocol incorrectly referred to the units for the determination of CCI CCI which have been reported as CCI by the central laboratory.

Section 4.7.4: The protocol states that the Negative Binomial Model will consider the log-time on study as offset. However, as specified in Section 4.1.7, NCFB Pulmonary Exacerbations analyses focus on the treatment period so log-time on treatment will be considered.

Sections 4.7.5 and 4.7.6.1: The protocol states that the CCI
[REDACTED]
[REDACTED]. Using date of first IMP as the start time of risk is considered to be biased, so date of randomisation will be used instead.

CONFIDENTIAL

Sponsor:	Zambon S.p.A.	Protocol Number:	Z7224L02
----------	---------------	------------------	----------

Section 4.7.6.1: The protocol states that the CCI [REDACTED] CCI [REDACTED] For time-to-event endpoints, generally the + 1 is not included because this overestimates the time by 1 day for every event, therefore “+ 1” has been deleted.

Section 4.7.6.5: The protocol states that the CCI [REDACTED] total score will be computed and analysed. However, as recommended in the Manual Scoring Instructions [REDACTED], only the CCI [REDACTED] domain scores will be presented and analysed.

There have been no other changes in analyses from those defined in the protocol.

CONFIDENTIAL

Sponsor:	Zambon S.p.A.	Protocol Number:	Z7224L02
----------	---------------	------------------	----------

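### SAP 4.7.6.6 divides by follow-up time to study completion but counts event days only up to treatment completion

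*SAP*

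**What the plan says.** SAP 4.1.7 defines two clocks that start at the first IMP dose.

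- Exposure time ends at treatment completion or discontinuation. For the efficacy analyses, "the exposure time will not include the time from end of treatment to the follow-up call".
- Follow-up time ends later, or at least elsewhere: "Follow-up time (days) = [date of study completion/discontinuation - date of first IMP dose + 1".

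SAP 4.7.6.6 uses follow-up time in both the numerator and the denominator of its formula and refers to 4.1.7 for the definition. It then says that, for an event resolving after treatment ends, "the number of days of duration after the treatment completion/discontinuation, i.e. out of the follow-up period" will be taken off the summed durations.

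Other sections bear on which clock was meant:

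- SAP 4.1.11 limits exacerbations by onset as well. Only those starting between the first dose and the "date of treatment completion/discontinuation will be considered in the analysis".
- SAP 4.7.6.1 says that subjects without an event "will be considered as censored at the time of their last follow-up, i.e. at the date of treatment completion/discontinuation".
- SAP 4.13 explains the offset of the primary model: "NCFB Pulmonary Exacerbations analyses focus on the treatment period so log-time on treatment will be considered".
- The descriptive table in 4.7.6.6 itself reports mean exposure time.
- SAP 4.7.6.8 deliberately takes follow-up duration instead of exposure as its offset.

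On the gap between the clocks, Protocol 9.6 states: "A follow-up phone call will be performed at 2 weeks" (± 3 days) after IMP is discontinued.

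**The concern.** The clause in 4.7.6.6 treats days after treatment completion as lying outside follow-up. Under 4.1.7 they lie inside it whenever study completion comes after treatment completion. A programmer who follows the cross-reference puts those days in the denominator, while the truncation rule keeps every event day out of them. If the redacted events are pulmonary exacerbations, as the reference to a resolution date suggests, 4.1.11 also removes events that begin there. The extra days can then only count as event-free.

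A programmer who follows the clause instead would stop both clocks at treatment completion. Two competent programmers could therefore produce different values for the same subject. What is at stake is the size of an annualised estimate, and whether this endpoint uses the treatment-period window that the SAP applies to its other efficacy analyses.

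**Working it through.** **Stated figure.** The plan gives no figure for this endpoint, so there is none to reproduce.

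**Inputs from the documents.** Treatment lasts 12 months (T = 365 days used). The call is at 14 days, range 11 to 17 (Protocol 9.6). The placebo rate is 1.09 per year and the effect 35% (Protocol section 3, Sample Size).

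**Assumptions.** A subject's study completion is the follow-up call. Event lengths of 14 and 21 days are illustrative.

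**Formula.** Let D be event days up to treatment completion and L the tail.

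- As written: E = 365.25 × (T + L − D) / (T + L), so annualised event days are 365.25 × D / (T + L).
- On exposure time: annualised event days are 365.25 × D / T.
- The ratio is T / (T + L), so the shrinkage is L / (T + L).

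| T (days) | L = 11 | L = 14 | L = 17 |
|---|---|---|---|
| 365 | 11/376 = 2.9% | 14/379 = 3.7% | 17/382 = 4.5% |
| 180 | 11/191 = 5.8% | 14/194 = 7.2% | 17/197 = 8.6% |
| 90 | 11/101 = 10.9% | 14/104 = 13.5% | 17/107 = 15.9% |

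The 180- and 90-day rows are illustrations. They apply only to a subject who has a tail of that length.

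**One subject.** With T = 365, D = 21 and L = 14, the formula as written gives 365.25 × 358/379 = 345.01. On exposure time it gives 365.25 × 344/365 = 344.24. The gap is 0.78 days a year before rounding.

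**Treatment difference.** Take 14-day events and T = 365.

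- Placebo event days are 1.09 × 14 × 365.25/365 = 15.27.
- Active event days are 0.65 × 15.27 = 9.93.
- The difference on exposure time is 5.34 days.
- As written, with a 14-day tail for everyone, it is 5.34 × 365/379 = 5.15 days.

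**Unequal tails.** Suppose 85% of active and 75% of placebo subjects have the tail. The difference is 9.93 × (0.85 × 0.963 + 0.15) subtracted from 14.85, the placebo value 15.27 × (0.75 × 0.963 + 0.25), which is 5.23 days. With the shares reversed it is 5.14. Under no treatment effect, a 10-point imbalance in tails moves the comparison by 0.10 × 0.037 × 15.27 = 0.06 days a year.

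**Power.** A simulation of 10,000 trials used 143 subjects per arm (287 randomised, SAP 3.9), a placebo rate of 1.09, 20% withdrawal and a 35% effect. It assumed dispersion 0.34, 16-day episodes with a 14-day gap, 30% of subjects closed at 90 to 364 days, a 14-day tail for all but dropouts, and treatment as the only model term.

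| | As written | Exposure time |
|---|---|---|
| Placebo event days | 14.5 | 15.1 |
| Treatment difference (days) | 4.75 | 4.94 |
| Power | 65.6% | 65.5% |

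Because the simulation gives closed-out subjects a tail, its shrinkage is on the high side if they have none.

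**The case against.** The strongest reply is that there may be no tail. No section says that a subject's study completion is the follow-up call. The Protocol summary calls Visit 7 the final visit, and Protocol 7.2 separates the last phone call from the point that ends the trial for the primary analysis. SAP 4.3 reports study completion and having the call as separate items. SAP 4.7.4.2 compares realised follow-up directly with expected exposure. SAP 4.7.6.1 and the clause in 4.7.6.6 both treat follow-up as ending with treatment. This stands to the extent that the size of the effect is conditional. It does not remove the contradiction: if the two clocks always coincided, 4.1.7 would not need both, and the choice made in 4.7.6.8 would mean little. SAP 3.1 also ties the end of the trial to the follow-up call.

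A reader might infer a much larger effect from early closure, since SAP 4.7.4.2 says: "The expected duration of exposure for some subjects will therefore be shorter than 365 days". The documents do not establish that. SAP 3.9 brings subjects back for Visit 7 or an early termination visit. SAP 4.1.7 dates treatment discontinuation at the End of Study Visit for those who leave before the End of Treatment Visit, so these subjects may have no tail.

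A reader might also infer that event-free padding favours the active arm. The arithmetic shows the reverse: a common tail attenuates a true difference.

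Finally, a reader might press for an exposure-weighted analysis, because an event-free first-dose withdrawal scores 365.25 at full weight. The documents give no such withdrawal rates by arm. Weighting also has its own bias when withdrawal depends on exacerbation risk differently by arm. That is a trade-off, not an error in the plan.

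**Conclusion.** Section 4.7.6.6 is inconsistent as written, and this needs no assumption: its description of the days it removes does not fit the definition it cites. The numerical consequence assumes that study completion is the follow-up call. On that basis annualised event days and any treatment difference are about 3.7% too small for a subject with 365 days' exposure (2.9% to 4.5%), and by more at shorter exposure only where a tail exists.

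The point is minor. Power does not change materially, and no directional bias of note is shown. The primary analysis is not affected, because SAP 4.7.4, 4.9 and 4.13 set its offset to time on treatment. The endpoint's name and its place in the testing hierarchy are redacted, so nothing is claimed about any conclusion.

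**What to change.** In SAP 4.7.6.6, replace follow-up time with exposure time (days) in both places in the formula and in the sentence that refers to 4.1.7. End the truncation clause with: i.e. after the end of exposure time. This matches the treatment-period window in 4.1.7, 4.1.11, 4.7.6.1 and 4.13.

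For consistency, make the same substitution for the primary endpoint in these places:

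- the follow-up reference in 4.7.1;
- the total follow-up time summarised in 4.7.4;
- the variable notes in 4.14 for the negative binomial model and for the multiple imputation code.

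Leave 4.7.6.8 as the stated exception, and say in the 4.14 negative binomial note that it is one.

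The cost is wording only, with no new data, model or table. It should be settled before unblinding, because SAP section 1 requires later deviations to be justified and marked post hoc. If the blind has already been broken, document the correction in that way.
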